**14.12      Appendix 12: Patient Global Impression of Prurigo Nodularis Severity (PGI-PN-S)**

Instructions: Please select the box that best describes the severity of your prurigo nodularis right now.

Right now, my prurigo nodularis is:

- 0    Absent (No sign or symptom of prurigo nodularis)
- 1    Minimal
- 2    Mild
- 3    Moderate
- 4    Severe

#### 14.13 Appendix 13: Summary of Changes (Version 6 compared to Version 5)

The following are changes to the KPL-716-C201 protocol (version 6 versus Version 5), which summarizes major changes to the protocol. Additional minor changes were also made with respect to typos, minor edits for clarification, adding new abbreviations to the list of abbreviations, and updating the table of contents.

Protocol Section	Modification	Rationale
First page + footer	Added/changed to Protocol Version 6, 19 July 2021 and included [REDACTED] to the Sponsor	New protocol version.
Synopsis	Removed Latin America	Removed as Sponsor will not be enrolling subjects in this region.
Synopsis, and Section 3.2	Proportion of subjects achieving 0 or 1 <del>from baseline</del> in PN-IGA at Week 16	Clarified the PN-IGA measures the overall assessment at Week 16.
Synopsis and Section 4.7.2	8. Presence of <del>moderately</del> severe depression as indicated by PHQ-9 total score of <del>≥15</del> 20 or item 9 score >0 at the Screening Visit or Day 1.	Revised to reduce screen failures. Some screen-failed subjects by PHQ-9 cut-off score of 15 from activated North America sites were confirmed to be non-depressive by psychiatrists. Currently revised to only exclude subjects who scored severe depression by PHQ-9.
Synopsis and Section 8.3	<del>Multiple comparison/Multiplicity There is a multiplicity adjustment planned for efficacy endpoints in Phase 2b. Details will be specified in the SAP.</del>  As this is a dose finding study, there is no multiplicity adjustment planned for the comparisons of multiple doses of KPL-716 versus placebo.	As this is a dose-ranging study and not intended to make label claims out of it, so multiplicity is not planned.
Synopsis	An interim analysis for Phase 2b portion may be conducted after at least 50% subjects complete Week 16 Visit. If the interim analysis is conducted in the Phase 2b part, a two-sided alpha of 0.0001 will be spent. The two-sided alpha level for the final Phase 2b efficacy analysis will be 0.05. Additional details regarding the interim analysis, if performed, will be provided in the SAP along with other analysis plans.	Added to align with Section 8.12.
Section 7.3.4	PN-NAT is a novel exploratory tool for the evaluation of disease severity based on estimate of the number of nodules over the whole body, estimate of hardness of <del>nodules over the whole body in representative area</del> , estimate of extent of excoriation over the whole body, distribution of nodules, exact number of nodules in the representative area. There are 5 components to PN-NAT.	Editorial alignment with Appendix 3.

Protocol Section	Modification	Rationale
Section 7.3.13	The PGIC ( Appendix 6: Patient Global Impression of Change (PGIC) ) is a patient-reported survey that assesses the subject's impression of change <del>in</del> on prurigo nodularis since the beginning of the study. Scoring ranges from 13: "very much improved" to 73: "very much <del>improved</del> worse."	Editorial alignment with Appendix 6.

Signature Page for [REDACTED]

Approval	[REDACTED]
	Clinical 19-Jul-2021 21:48:21 GMT+0000

Signature Page for [REDACTED]

PN-NAT	Prurigo Nodularis Nodule Assessment Tool
PN-IGA	Prurigo Nodularis Investigator Global Assessment
PP	Per protocol
PT	Preferred term
Q1	First quartile
Q3	Third quartile
Q4W	Every Four (4) Weeks
QoL	Quality of life
QT	Electrocardiographic interval from the beginning of the QRS complex to the end of the T wave
QTcB	QT interval corrected for heart rate using Bazett's method
QTcF	QT interval corrected for heart rate using Fridericia's method
SAE	Serious adverse experience/event
SAP	Statistical Analysis Plan
SC	Subcutaneous
SD	Standard deviation
SE	Standard error
SOC	System organ class
TEAE	Treatment-emergent adverse event
TCS	Topical corticosteroid
VAS	Visual Analog Scale
WHO	World Health Organization
WHODRUG	World Health Organization Drug Dictionary
WI-NRS	Worst Itch Numeric Rating Scale
WOCF	Worst Observation Carried Forward

1. INTRODUCTION

This Statistical Analysis Plan (SAP) contains a detailed description of data presentations, statistical analysis methods, and data reporting specifications for the programming outputs and preparation of the Clinical Study Report (CSR) for the Phase 2b portion of study KPL-716-C201. The SAP for the phase 2a portion was already prepared separately.

The SAP is based on the protocol KPL-716-C201 version 6 dated 19 Jul 2021, KPL-716-C201 protocol European version 1.0 dated 06AUG2021, and KPL-716-C201 protocol, UK-Specific version 2.0 dated 18AUG2021.

1.1. Study Objectives

1.1.1. Primary objective

- To evaluate the efficacy of subcutaneous (SC) KPL-716 vs. placebo in reducing pruritus in Prurigo Nodularis (PN) subjects experiencing severe pruritus

1.1.2. Secondary objectives

- To evaluate the effect of SC KPL-716 vs. placebo in improving sleep in PN subjects experiencing severe pruritus
- To evaluate the efficacy of SC KPL-716 vs. placebo in improving quality of life in PN subjects experiencing severe pruritus
- To evaluate the effect of SC KPL-716 vs. placebo in reducing disease severity in PN subjects experiencing severe pruritus
- To evaluate the safety and tolerability of SC KPL-716 vs. placebo in PN subjects experiencing severe pruritus
- To evaluate the pharmacokinetics (PK) of SC KPL-716 in PN subjects experiencing severe pruritus

1.1.3. Exploratory objectives

- To evaluate the immunogenicity of SC KPL-716 in PN subjects experiencing severe pruritus
- To evaluate the effect of KPL-716 vs. placebo on skin and blood biomarkers
- To evaluate the correlation between KPL-716 responsiveness and co-morbidities in PN

1.2. Study Design

This is a randomized, double-blind, placebo-controlled study to investigate the efficacy, safety, tolerability, PK, and immunogenicity of KPL-716 administered SC in subjects with moderate to severe PN experiencing severe pruritus.

[figure not shown]
The Phase 2b study ([Figure 1](#)) consists of a 4-week screening period and a 16-week double-blind (DB) period, followed by a 36-week open-label-extension (OLE) period. Approximately 180

subjects with moderate to severe PN experiencing severe pruritus will be randomized (at 1:1:1:1 ratio) into one of the following 4 arms:

- Arm A: KPL-716, 540 mg, SC, every 4 weeks (Q4W)
- Arm B: KPL-716, 360 mg, SC, Q4W
- Arm C: KPL-716, 120 mg, SC, Q4W
- Arm D: Placebo, SC, Q4W

A total of 4 doses of study drug will be administered during the DB Period to measure the efficacy, safety, and PK of KPL-716.

Figure 1 Phase 2b Study Design Diagram

After the DB period, all subjects will have the option to receive KPL-716 360 mg SC, Q2W during the OLE period to evaluate the long-term safety and PK of KPL-716. For subjects who complete the DB period but choose not to participate in OLE, or who terminate earlier, an End of Study (EOS) visit will be required 4 weeks following the date of last study drug dose.

Subjects will follow the schedule below:

- Screening period (minimum 7 days and maximum 28 days)
- DB period (Day 1 [Baseline] to Week 16)
- OLE period (End of Week 16 to Week 52)

The allowable visit window from Week 2 to Week 16 is \pm 2 days and thereafter to Week 52 is \pm 3 days.

Randomization and Dosing:

Subjects will be randomized 1:1:1:1 into one of the following 4 arms: KPL-716 540 mg SC, Q4W; KPL-716 360 mg SC, Q4W; KPL-716 120 mg SC, Q4W; or placebo SC, Q4W. At the end of DB period, all subjects will have the option to enter the OLE period to receive KPL-716

360 mg SC Q2W. Stratification will be performed based on sex and years since first nodule observed (i.e., ≥ 10 years vs. < 10 years).

Efficacy Assessments:

Efficacy in reduction of pruritus will be assessed via daily recording of the Worst Itch Numeric Rating Scale (WI-NRS). Efficacy in improvement of sleep will be assessed via Sleep Loss Visual Analog Scale (VAS). Impact on quality of life will be assessed via Itchy Quality of Life (ItchyQoL). Depression and anxiety will be assessed based on Patient Health Questionnaire-9 (PHQ-9) and General Anxiety Disorder-7 (GAD-7). Impact on disease severity will be followed by Prurigo Nodularis Investigator Global Assessment (PN-IGA), Prurigo Nodularis Nodule Assessment Tool (PN-NAT), Investigator's Global Assessment for Prurigo Nodularis-Stage (IGA-CNPG-S), Investigator's Global Assessment for Prurigo Nodularis-Activity (IGA-CNPG-A), Patient Global Impression of Prurigo Nodularis Severity (PGI-PN-S), and Patient Global Impression of Change (PGIC). Schedules of these efficacy assessments and related tools are included in the Protocol appendices.

- WI-NRS score: The daily diary contains one numerical rating scale to assess subjects' pruritus (WI-NRS) and one Yes/No question regarding the use of rescue medication for itch relief. Subjects will be asked to assign a numerical score to the intensity of their most severe (worst) pruritus using a scale from 0 to 10, with 0 indicating no pruritus and 10 indicating the worst imaginable pruritus. This pruritus NRS will be used to assess subjects' daily level of worst pruritus from the Screening Visit through the EOS Visit.
- PN-IGA: This is a novel exploratory tool for the overall assessment of PN disease severity based on the elevation of the nodules and number of elevated nodules. The PN-IGA will be performed by the Investigator. The PN-IGA utilizes a 5-point scale that ranges from 0 (clear) to 4 (severe). Subjects may present with smaller papular lesions, scarring, or post-inflammatory hyper- or hypopigmentation of the skin, which are not considered as part of this assessment. A PN-IGA score is assigned based on the appearance of the disease at the time of evaluation without referring to the baseline state. Every effort will be made for the same Investigator to assess PN-IGA over time.
- IGA-CNPG-S: This is a novel tool for the assessment of PN disease severity based on the number of palpable nodules. The IGA-CNPG-S will be performed by the Investigator. The IGA-CNPG-S utilizes a 5-point scale that ranges from 0 (clear) to 4 (severe). A score is assigned based on the appearance of the disease at the time of evaluation without referring to the baseline state. Every effort will be made for the same Investigator to assess IGA-CNPG-S over time.
- Sleep Loss VAS: Subjects will be asked to place a line perpendicular to the VAS line at the point that represents the intensity of their average sleeplessness experienced over the previous 3 nights using a scale from 0 to 10, with 0 indicating no sleeplessness and 10 indicating the worst imaginable sleeplessness. The Sleep Loss VAS is administered per the Schedule of Activities.
- ItchyQoL: This tool focuses on the impact of pruritus on daily activities and on the level of psychological stress. It contains 22 items. The frequency items are scored

using a 5-point Likert scale ranging from “never” to “all the time.” The bother items are scored from 1 (not bothered) to 5 (severely bothered). The recall period in ItchyQoL is the past week. The ItchyQoL total score is defined as the sum of all 22 item scores. The ItchyQoL-symptom subscale score is calculated as the sum of items 1-6. The ItchyQoL-functional subscale score is calculated as the sum of items 7-13. The ItchyQoL-emotional subscale score is calculated as the sum of items 14-22. For each subscale, if more than 50% of items have missing values, the subscale will be set to missing and no total score will be calculated. If items with missing values are equal to or less than 50%, the subscale will be prorated based on items with non-missing values. Subscale can be rounded into integer after proration. Total scores can be classified as little (≤ 30), mild (31-50), moderate (51-80), or severe (81-110).

- IGA-CNPG-A is a novel tool for the assessment of PN disease activity based on the proportion of nodules with excoriations and crusts. The IGA-CNPG-A will be performed by the Investigator. The IGA-CNPG-A utilizes a 5-point scale that ranges from 0 (clear) to 4 (severe). A score is assigned based on the appearance of the disease at the time of the evaluation without referring to the baseline state. Every effort will be made for the same Investigator to assess IGA-CNPG-A over time.
- PN-NAT: This is a novel exploratory tool for the evaluation of disease severity based on 5 components:
 1. estimate of the number of nodules over the whole body,
 2. estimate of hardness of nodules in the representative area,
 3. estimate of extent of excoriation over the whole body,
 4. distribution of nodules,
 5. exact nodules count in the representative area.

Subjects may present with smaller papular lesions, scarring, or post-inflammatory hyper- or hypo-pigmentation of the skin, which are not considered as part of this assessment. A score is assigned to each component based on the appearance of the disease at the time of the evaluation without referring to the baseline state. Given its exploratory nature, subtotal score of the first three components will be calculated while distribution of nodules and exact nodule count in the representative area will be analyzed separately.

- The PHQ-9 is a subject-reported measure that assesses the subject’s general mental health. The PHQ-9 contains 9 items scored on a Likert scale ranging from 0: “not at all” to 3: “nearly every day.” The recall period is the last 2 weeks. The PHQ-9 will be administered at designated visits.
- The GAD-7 is a subject-reported survey that assesses the subject’s level of anxiety. The GAD-7 contains 7 items scored on a Likert scale ranging from 0: “not at all” to 3: “nearly every day.” The recall period is the last 2 weeks. The GAD-7 will be administered at designated visits.

- The PGI-PN-S is a subject-reported questionnaire that assesses the subject's impression of PN disease severity at the time of evaluation. It is scored from 0: "absent (no sign or symptom of prurigo nodularis)" to 4: "severe."
- The PGIC is a subject-reported survey that assesses the subject's impression of change in their PN disease since the beginning of the study. Scoring ranges from 1: "very much improved" to 7: "very much worse".

1.3. Study Endpoints

1.3.1. Efficacy Endpoints

1.3.1.1. Primary Endpoint

- Percent change from baseline in weekly average Worst Itch–Numeric Rating Scale (WI-NRS) at Week 16

1.3.1.2. Key Secondary Endpoints

- Proportion of subjects achieving at least a 4-point reduction from baseline in weekly average WI-NRS at Week 16
- Proportion of subjects achieving clear (0) or almost clear (1) in PN-IGA at Week 16
- Proportion of subjects achieving at least a 6-point reduction from baseline in weekly average WI-NRS at Week 16

1.3.1.3. Other Secondary Efficacy Endpoints

Related to pruritus:

- Change and percent change from baseline in weekly average of WI-NRS over time
- Proportion of subjects achieving at least a 6-point reduction from baseline in weekly average WI-NRS over time
- Proportion of subjects achieving at least a 4-point reduction from baseline in weekly average WI-NRS over time

Related to disease severity:

- Proportion of subjects achieving clear (0) or almost clear (1) in PN-IGA over time
- Proportion of subjects with at least 2-point improvement from baseline in PN-IGA over time
- Proportion of subjects achieving clear (0) or almost clear (1) in Investigator's Global Assessment for Prurigo Nodularis-Stage (IGA-CNPG-S) over time
- Proportion of subjects with at least 2-point improvement from baseline in IGA-CNPG-S over time

Related to sleep:

- Change and percent change from baseline in weekly average of Sleep Loss Visual Analog Scale (VAS) over time

Related to quality of life:

- Change and percent change from baseline in ItchyQoL over time

1.3.1.4. Exploratory Endpoints

- Proportion of subjects achieving clear (0) or almost clear (1) in IGA-CNPG-Activity (IGA-CNPG-A) over time
- Change from baseline in Prurigo Nodularis Nodule Assessment Tool (PN-NAT) over time
- Change from baseline in the total score of Patient Health Questionnaire (PHQ-9) over time
- Change from baseline in the total score of General Anxiety Disorder (GAD-7) over time
- Days and proportion of subjects using rescue medication over time
- Patient Global Impression of Prurigo Nodularis Severity (PGI-PN-S) over time
- Patient Global Impression of Change (PGIC) over time
- Change from baseline in skin and blood biomarkers over time

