#### 3.3 Other Secondary Efficacy Endpoints for Phase 2b

Related to pruritus:

- Change and percent change from baseline in weekly average of WI-NRS over time
- Proportion of subjects achieving at least a 6-point reduction from baseline in weekly average WI-NRS over time.
- Proportion of subjects achieving at least a 4-point reduction from baseline in weekly average WI-NRS over time.

Related to disease severity:

- Proportion of subjects achieving 0 or 1 in PN-IGA over time
- Proportion of subjects with at least 2-point improvement from baseline in PN-IGA over time
- Proportion of subjects achieving 0 or 1 in Investigator's Global Assessment for Prurigo Nodularis-Stage (IGA-CNPG-S) over time
- Proportion of subjects with at least 2-point improvement from baseline in IGA-CNPG-S over time

Related to sleep:

- Change and percent change from baseline in weekly average of Sleep Loss Visual Analog Scale (VAS) over time

Related to quality of life:

- Change and percent change from baseline in ItchyQoL over time

Exploratory Efficacy Measures:

- Proportion of subjects achieving 0 or 1 in IGA-CNPG-Activity (IGA-CNPG-A) over time
- Change from baseline in Prurigo Nodularis Nodule Assessment Tool (PN-NAT) over time

- Change from baseline in the total score of Patient Health Questionnaire (PHQ-9) over time
- Change from baseline in the total score of General Anxiety Disorder (GAD-7) over time
- Days and proportion of subjects using rescue medication over time
- Patient Global Impression of Prurigo Nodularis Severity (PGI-PN-S) over time
- Patient Global Impression of Change (PGIC) over time
- Change from baseline in skin and blood biomarkers over time

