### **4.7 Selection of Study Population**

#### **4.7.1 Inclusion Criteria**

1. Male or female aged 18 to 80 years, inclusive, at the time of consent.
2. Have a physician-documented diagnosis of PN that is confirmed by review of medical photography (as outlined in the Study Manual) during the Screening Period. Duration of PN (since the time of first PN nodule) must be at least 6 months from the time of first PN nodule to Day 1, as affirmed by the subject.
3. Have at least 20 nodules of approximately 0.5 to 2 cm at the Screening Visit and Day 1. The nodules must be pruritic and present on at least 2 different anatomical locations (not be localized), involve the extremities, with extensor extremity involvement greater than the flexor extremity involvement. Nodules on the head (face and scalp) are not counted as an anatomical location for eligibility criteria. Each arm, each leg, and trunk are considered different anatomical locations.
4. Subject has severe pruritus, defined as WI-NRS  $\geq 7$  at the Screening Visit and a mean weekly WI-NRS  $\geq 7$  for the week (7 consecutive days) immediately prior to randomization (at least 5 days of recordings) on eDiary.
5. PN-IGA score of  $\geq 3$  (on a scale of 0-4, in which 3 is moderate and 4 is severe) at Screening and Baseline Visits.
6. Sexually active female subjects must be:
  - postmenopausal, defined as at least 12 consecutive months post cessation of menses (without an alternative medical cause) and confirmed by a follicular stimulating hormone (FSH) test, or

- surgically sterile following documented hysterectomy, bilateral salpingectomy, bilateral oophorectomy or
- nonpregnant, nonlactating, and having agreed to use a highly effective method of contraception from the Screening Visit until 16 weeks after final study drug administration.
  - Note: highly effective methods of contraception include:
    - hormonal contraceptives associated with inhibition of ovulation (stable dose for at least 4 weeks prior to first dose)
    - intrauterine device
    - intrauterine system
    - double barrier methods of contraception (barrier methods include male condom, female condom, cervical cap, diaphragm, contraceptive sponge) in conjunction with spermicide.
    - tubal ligation
    - vasectomized male partner

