### 7.3.7 Investigator's Global Assessment of Prurigo Nodularis-Activity (IGA-CNPG-A)

IGA-CNPG-A is a novel tool for the assessment of PN disease activity based on the proportion of nodules with excoriations and crusts. The IGA will be performed by the Investigator. The IGA utilizes a 5-point scale that ranges from 0 (clear) to 4 (severe). A score is assigned based on the appearance of the disease at the time of the evaluation without referring to the baseline state. Every effort will be made for the same Investigator to assess IGA-CNPG-A over time. The IGA-CNPG-A is provided in [Appendix 8: Investigator's Global Assessment for Prurigo Nodularis-Activity \(IGA-CNPG-A\)](#). The IGA-CNPG-A tool is administered at designated visits.

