**IGA Chronic Nodular Prurigo Activity® (IGA-CNPG A)**

**Version 2.0 (December 06 2018)**

Score	Category	Description: Activity (IGA-CNPG A)
0	Clear	No nodules have excoriations or crusts
1	Almost Clear	Very small proportion of nodules have excoriations or crusts (up to approximately 10% of all nodules)
2	Mild	Minority of nodules have excoriations or crusts (approximately 11- 25% of all nodules)
3	Moderate	Many nodules have excoriations or crusts (approximately 26- 75% of all nodules)
4	Severe	Majority of nodules have excoriations or crusts (approximately 76-100% of all nodules)

14.9

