4.6.4. Analysis of Other Efficacy Endpoints

The primary estimand for continuous endpoints of change and percent change from baseline specified as secondary and exploratory endpoints will be defined and analyzed as the primary estimand for primary efficacy endpoints. If some extreme small values are observed at baseline for a parameter, percent changes will not be summarized for that parameter due to inflated percent change. For example, preliminary data showed values of 0 for some subjects in sleep loss VAS.

The primary estimand for binary responder endpoints over time including week 16 will be defined and analyzed as key secondary efficacy endpoints above.

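### IGA-CNPG-A has no entry minimum, so subjects who start and stay at 0 or 1 count as responders without improving, which dilutes this exploratory endpoint

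*SAP*

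**What the plan says.** The endpoint appears in SAP 1.3.1.4 as "Proportion of subjects achieving clear (0) or almost clear (1) in IGA-CNPG-Activity (IGA-CNPG-A) over time" and in Protocol 3.3, among the exploratory measures, as "Proportion of subjects achieving 0 or 1 in IGA-CNPG-Activity (IGA-CNPG-A) over time". Neither version sets a condition on the baseline score or asks for a change from it.

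Protocol 7.3.7 describes the scale as "based on the proportion of nodules with excoriations and crusts" and adds: "A score is assigned based on the appearance of the disease at the time of the evaluation without referring to the baseline state". In Protocol Appendix 8, grade 0 reads "No nodules have excoriations or crusts" and grade 1 reads "Very small proportion of nodules have excoriations or crusts (up to approximately 10% of all nodules".

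Protocol 4.7.1 requires a PN-IGA of at least 3, "on a scale of 0-4, in which 3 is moderate and 4 is severe) at Screening and Baseline Visits". It also requires at least 20 pruritic nodules and a WI-NRS of at least 7. Neither the inclusion list (4.7.1) nor the exclusion list (4.7.2) mentions IGA-CNPG-A, excoriation or crusts.

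For the analysis, SAP 4.6 places all efficacy analyses in the mITT set, and SAP 4.6.4 states: "The primary estimand for binary responder endpoints over time including week 16 will be defined and analyzed as key secondary efficacy endpoints above". The key secondary rules (SAP 4.6.3) make a subject a non-responder after rescue or prohibited medication that affects efficacy, or when the value is missing. They use a CMH test stratified by sex and years since first nodule.

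**The concern.** A 0-or-1 endpoint reads as improvement only if nobody starts at 0 or 1. For two of the three investigator scales analysed this way, the entry criteria ensure that. For IGA-CNPG-A they do not, and nothing in the responder rule makes up for it. PN-IGA and IGA-CNPG-S each also have a responder endpoint requiring at least a 2-point gain from baseline (SAP 1.3.1.3); IGA-CNPG-A has none.

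Subjects who start at 0 or 1 and stay there would raise the response rate in every arm, placebo included, and pull the arms closer together. In a dose-finding study the separation between arms is what the reader looks for. Baseline IGA-CNPG-A is not among the baseline characteristics listed in SAP 4.2.2, so that table would not show how many such subjects there are.

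**Working it through.** **Step 1. Which baseline scores can enter?**

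| Scale | What it grades | Entry criterion that bears on it | Baseline 0 or 1 possible? |
|---|---|---|---|
| PN-IGA | share of nodules that are severely elevated | PN-IGA at least 3 | No |
| IGA-CNPG-S | number of palpable nodules (grade 3 is about 20 to 100) | at least 20 nodules | In effect no |
| IGA-CNPG-A | share of nodules with excoriations or crusts | none | Yes |

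Example: 20 elevated, itchy nodules of which 2 are excoriated gives 2/20 = 10%, which is grade 1. PN-NAT (Protocol Appendix 3) likewise scores excoriation separately from nodule number and allows for none.

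**Step 2. The plan's own figure.** The documents state no rate or power for this endpoint. The only figure used here is the arm size in SAP 1.5. A two-sample t-test with a difference of 23, SD 35 and two-sided alpha 0.05 needs 37.3, so 38 per arm (power 80.7%). Then 38/0.85 = 44.7, so 45 per arm. The plan's figure reproduces.

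**Step 3. Dilution.** Let q be the share at 0 or 1 at baseline, all of whom stay there, and p the response rate among the others. The observed rate is q + (1-q)p, and the difference is (1-q)(p1 - p0). With assumed rates of 50% and 20%:

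| q | Active | Placebo | Difference |
|---|---|---|---|
| 0 | 50% | 20% | 30 points |
| 2% | 0.02 + 0.98 x 0.50 = 51.0% | 0.02 + 0.98 x 0.20 = 21.6% | 29.4 |
| 5% | 52.5% | 24.0% | 28.5 |
| 10% | 55.0% | 28.0% | 27.0 |
| 20% | 60.0% | 36.0% | 24.0 |

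If only a fraction r of the baseline 0/1 subjects remain responders, the difference becomes (1-q)(p1 - p0) + q(r1 - r0). When r is equal in both arms it cancels and the factor (1-q) stands. If the drug holds more of them at 0/1 than placebo does, the dilution is smaller: q = 10%, r1 = 1.0, r0 = 0.8 gives 0.9 x 30 + 0.1 x 20 = 29 points.

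**Step 4. Power, for illustration.** Assumptions: 45 per arm, all baseline 0/1 subjects stay there, and the rates shown apply to subjects who start at 2 or more, after the non-responder rules. The restricted analysis has 45(1-q) per arm: 42.8, 40.5 and 36.

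| q | 35% vs 10%: all mITT | 35% vs 10%: baseline at least 2 | 45% vs 20%: all mITT | 45% vs 20%: baseline at least 2 |
|---|---|---|---|---|
| 0 | 82% | 82% | 72% | 72% |
| 5% | 73% | 80% | 66% | 70% |
| 10% | 65% | 78% | 59% | 68% |
| 20% | 50% | 73% | 48% | 62% |

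In each of these scenarios with q above zero, restriction gains more from the undiluted difference than it loses from the smaller denominator.

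**The case against.** The strongest reply is that the affected group may be negligible. Entry demands severe itch and at least 20 pruritic nodules, and Protocol 1.1 describes a disease driven by intense scratching, so few subjects may have 10% or fewer of their nodules excoriated. This stands. Nothing in the documents supports 20%, or any other value, and at q = 2% the loss is 0.6 points out of 30.

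A reader might infer more than the text supports in three respects.

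- **A spurious treatment effect.** An excess of 3 such subjects in one of two arms of 45 is 3/45 = 6.7 points, which looks alarming. But the arms are randomised. At q = 10% the SD of the difference in counts is sqrt(2 x 45 x 0.1 x 0.9) = 2.8, so an excess of 3 is about one SD. That is ordinary sampling variation, already reflected in the p-value and confidence interval. It neither biases the comparison nor inflates type I error.
- **Automatic response at every visit.** The rescue-medication and missing-data rules turn such subjects into non-responders, and so does a score above 1.
- **The undiluted 30 points as the one true effect.** In the whole mITT set, (1-q) x 30 is the true difference in the proportion at 0 or 1, given the assumption in Step 3. The 30 belongs to the subset starting at 2 or more. An absolute-status endpoint is coherent for a scale scored without reference to baseline; it simply does not measure improvement.

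Change in PN-NAT is a partial check, since it contains an excoriation item. SAP 1.2 adds that item to nodule number and hardness, so the check is not a clean one. Protocol 8.1 promises descriptive statistics for all endpoints and SAP Table 4 has a baseline window for this scale, so a baseline display by arm may appear, but it is not explicitly promised. Restricting the denominator also drops subjects who start at 0/1 and worsen, which is a fair reason to keep the full-set proportion in view.

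**Conclusion.** The gap is real and follows from the text alone: entry leaves IGA-CNPG-A free from 0 to 4, and the responder rule has no baseline condition. The expected consequence is a higher response rate in every arm, a drug-placebo difference diluted by about (1-q), and added noise.

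The size depends wholly on q, which the documents do not give, and on how many of these subjects stay at 0 or 1 in each arm. The figures above are illustrations, not estimates for this trial. The endpoint is exploratory, has no decision rule attached, and bears on neither the primary nor the key secondary results. This is a minor improvement worth making because it is cheap.

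**What to change.** In SAP 1.3.1.4 and 4.6.4, analyse IGA-CNPG-A 0/1 response among mITT subjects with a baseline IGA-CNPG-A of at least 2, keeping the same rescue and missing-data rules and the same CMH test. The subset is defined before treatment, so the randomised comparison is preserved.

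Report the all-mITT proportion beside it as a descriptive companion, so that subjects who start at 0/1 and worsen remain visible. Tabulate baseline IGA-CNPG-A by arm.

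The cost is a few SAP sentences and one short table. No new data are needed, because the schedule of activities already collects the scale at Screening and Baseline. The downside is a slightly smaller denominator for this one endpoint. If no subject starts at 0 or 1, the restricted and all-mITT results coincide.
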